Data Storage and Confidentiality

Many steps will be taken to ensure the security and integrity of all study data. Information obtained for this study will be stored on password-protected research drives. Data obtained from surveys, the BH and VA CDW, and the local EMR will be coded and stored separately from their code key files on a secured, password-protected, HIPAA compliant network drive. Only the Research Director, Project Manager and Evaluator will have access to the subjects' codes. Once coded, the de-identified data will be securely transferred to a password-protected, shared research drive for analysis. Hard copies of surveys returned from patients will be locked in a secure cabinet or drawer located in the team's research space. A waiver of authorization for both recruitment/identification purposes and for study procedures has been sought.

Audio recordings of the in-person interviews with an anticipated 60 subjects will be taped using approved recording devices, which will be stored in a locked cabinet or drawer. Interview recordings will be transcribed without identifiers. We will present informed consent forms and audio/visual consent forms (VA form 3203 “Consent for Use of Picture and/or Audio” and NYU Research Subject Audio/Video/Photo Use Consent Form) to all staff participants involved in qualitative research interviews who verbally consent to participate in the protocol.

Risk/Benefit Assessment

Risk

The main risk to patients, primary care and other staff, practice administrators, CHWs, and key informants, though unlikely, is a loss of confidentiality.

Protection Against Risks

Provider /staff participants will be asked to participate in the different parts of the study (CHW intervention, surveys) but not required to do so. Patient survey respondents will be offered a modest incentive (\$11 MetroCard) to compensate them for their time. Questionnaires and interviews will be delivered by a neutral party not in the employee’s supervisory chain. Participation is completely voluntary and participants may drop out of the study at any time.

For the neighborhood effects analysis, patients’ location information will be maintained at the level of the neighborhood, which is an aggregate of census tracts. NYC has over 2,100 census tracts. The NYC Department of City Planning constructs approximately 210 Neighborhood Tabulation Areas (NTA) out of the 2,100+ census tracts by aggregating whole census tracts. Although individual patient data is initially mapped to census tract level, it is used and analyzed only at the NTA level. Each NTA includes an average of about 50,000 residents. Patients’ precise geographic location therefore will not be identifiable. Seeking consent from patients for their data to be used for this study would increase the likelihood of loss of confidentiality.

Potential Benefits to the Subjects

Staff subjects may improve their clinical practice if they are randomized to the intervention, which provides a CHW to the PC provider that assists in accessing and interpreting the large VA and Bellevue electronic datasets in attempt to enhance patient care. Patients may receive improved care as a result of their providers receiving the information in an organized, usable fashion and having support to encourage patients to enroll in and complete programs that reduce the risk of developing type 2 DM. Potential risks are minimal and primarily include loss of confidentiality, while the potential benefit to individual and scientific knowledge is sizeable. CHWs will not be making any management decisions for patients’ care but rather will be acting under the direction of each patient’s primary care physician. CHWs who participate in interviews will gain opportunities to reflect upon the challenges and successes of their work and subsequently incorporate this understanding into their work, thus providing improved counseling and support to patients.

Investigator’s Qualifications & Experience

See attached biosketches for qualifications and experience.

Subject Identification, Recruitment and Consent/Assent

Method of Subject Identification and Recruitment, and Consent

All primary care staff will be given information about the proposed research during regular staff meetings, email announcements and a study flyer and then asked to participate. Staff providing verbal consent to participate will be randomized (as part of their PACT team) to either work with a CHW or serve as controls. Staff who opt-out will not be randomized, although might still work on a team that is included in the study. For example, if one primary care provider in a team declines participation, the other providers and team members consent, the team will be randomized to a study arm. If that team is randomized to an intervention arm, the

CHW would only work with the patients of the consenting providers. We anticipate that we will be able to obtain sufficient numbers of staff consenting to participate, as in our previous panel management study only one PCP out of fifty-one declined, and a majority of staff reported that the interventions and CHW support were helpful. Lastly, as CHWs will be extending services and interventions that are a part of regular, evidence-based practice on behalf of patients' primary care physician, patients will not individually consent to receiving phone calls, mailings, or any other contact with the CHW. For surveys, which are research procedures specific to this study, consenting elements will be presented at the top of the survey. Primary care teams will pre-approve all lists of patients receiving interventions as well as approving the content of the CHW's intervention. Patients will have the right to opt out of receiving outreach at any time. All mail materials will include instructions on how to stop receiving mail from the CHW.

A waiver of authorization for both recruitment/identification purposes and for study procedures has been sought. We use the electronic medical record to generate a list of eligible participants, in order to approach them to screen for eligibility. Without the requested Waiver, screening could not be practically carried out and would adversely affect the scientific rigor of the study.

A waiver of consent has been requested. Informed consent is given when a provider chooses to participate in the intervention. He or she can opt out of the study at any point. With regard to surveys, completion of the survey will serve as implied consent. The survey cover sheet includes all elements of consent. Informed consent is implied by patients completing and returning a mail-based survey. Similar to the staff survey, all patient surveys will state that the survey is voluntary, all data will be reported in the aggregate, and completion of the survey serves as consent for participation. The survey will also specify that completion of the survey will not impact their health care in any way and that their individual responses will not be shared with members of their health care team.

Further, patients will be considered to have given informed consent by choosing to continue to interact with CHWs. Patients can request to not be contacted by a team's CHW at any point. This will be clearly stated on all materials given to staff and patients. Interventions will consist of educating patients of existing services at the institution or outside of the institution that they can access to improve their health, ensuring coordination and follow-up on referrals already made by their health care team. Patients interested in attending a institution-provided service (such as MOVE, smoking cessation classes, or Telehealth) will be referred as a part of usual care from their team. Programs such as YMCA DPP are available to anyone that meets pre-diabetes criteria, not just our subjects. Anyone is able to join these programs without the referral of a physician. The study team will only offer existing evidence-based services already available to pre-diabetics. Patients interested in attending the community based DPP will be provided contact information or a warm transfer by telephone, but will need to register themselves and consent to the outside program. PHI will not be sent to either organization by the study team. Patients will be making an informed decision to join such groups and will be explicitly explained this via phone or letter. This same implied consent applies to patients who register for VA's Telehealth or MOVE services and BH's Healthy Lifestyle services.

CHWs will be interviewed in groups and/or individually, as they prefer. Their participation in interviews is voluntary. Identifying information on CHWs or on our study team members will not be collected or recorded in these interviews and observations.

Costs to the Subject

Subjects or their health insurance may be billed for the costs of medical care during this study if these expenses would have happened even if they were not in the study, or if your insurance agrees in advance to pay.

Payment for Participation

Patient survey respondents will be offered a modest incentive (\$ 11 MetroCard) to compensate them for their time.

Documentation of Consent

We will present informed consent forms and audio/visual consent forms (VA form 3203 “Consent for Use of Picture and/or Audio” and NYU Research Subject Audio/Video/Photo Use Consent Form) to all staff participants involved in qualitative research interviews who verbally consent to participate in the protocol. We will not be obtaining informed consent from those who will not be audiotaped. The consent will be obtained immediately prior to starting the interview.

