- 4. Develop, implement and assess strategies to recruit, train, and integrate peer CHW health coaches within the PCMH model.

The 36-month intervention will be conducted using a staggered entry design across four, overlapping, 12-month waves to account for CHW caseload limits. This study will test a scalable model of peer health coaching to address the millions of patients at risk for DM, using low cost, culturally congruent personnel to promote prevention of DM in PCMH practice. If successful, our study team will work with VA's Central Office and NY City's Health and Hospital Corporation to translate the model for larger scale implementation.

Characteristics of the Research Population

Number of Subjects

All 12 PC teams at VA NY Harbor and all 4 PCMH teams at BH will be eligible to participate. In our VA PROVE study, 51/52 PCPs participated in the intervention, and we expect similar rates in this project. Eligible patients will be identified through the study's pre-DM registry, which will be based on the EMR and Corporate Data Warehouse (CDW) at each site. This methodology builds on our ongoing national, retrospective cohort study of predictors of DM among veterans with pre-DM back to 2008. Based on preliminary analysis of VA NYHHS data from 2010-2012, 62% of veterans enrolled in PC without DM, have had an HbA1c test in the previous two years.

In the intervention group, we anticipate contacting 2,100 randomly selected patients (1,050 at the VA* and 1,050 at BH) to ultimately enroll about 1,100 patients (550 at the VA and 550 at BH). This outreach sample reflects our assumption that 20% of patients will be unreachable and that 60% of those reached will enroll in the study. Another 1,100 patients attributed to control group providers will be randomly selected as the control group, in accordance with the waiver of HIPAA authorization. As detailed below, the control group will not participate in the CHW intervention. The total sample, including the intervention and control groups, will be about 2,200 patients. This amounts to approximately 265 patients (across intervention and control groups) per wave and per clinical site.

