Data from the FACETS neighborhood database of social determinants will be conjoined with study data to describe whether contextual factors pertaining to NYC neighborhoods are associated with prediabetes prevalence across neighborhoods. We will use a multilevel statistical model, with patients nested within neighborhoods, to conduct this analysis.

Process Evaluation: To ensure that the intervention was delivered completely and standardized across the sites, CHWs and clinical teams, there will be continuous monitoring of process outcomes and fidelity to the protocol during the CHW intervention. We will maintain standardized protocols for each toolkit strategy and documentation of peer coaching. The CHW Coordinator will conduct quarterly assessments of the interventions, proportion of patients reached and engaged by site and CHW, fidelity to counseling protocols, and the preferred toolkit and contact strategies.

Statistical Power and Sample Size

The primary study outcome for power calculations is the annual hazard rate of incident DM.

To determine sample size, we begin with the total accessible population of about 46,000 primary care patients served at the two sites (BH and VA). Of these we exclude patients with diagnosed DM (25% at VA and 15% at BH) and those over 75 years of age (who are ineligible for this intervention). Of these eligible subjects, we estimated that about 70% will have had the HbA1c test in the last 2 years and that about 40% of these will have had a test result in the prediabetes range.

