While the above inclusion and exclusion criteria return about 9,300 eligible patients, 8,200 at BH and 1,100 at the VA, CHW caseload limitations preclude us from reaching all these eligible patients during the 3-year intervention. Assuming a caseload of 72 patients per fulltime CHW per wave (with 3.5 fulltime equivalent CHWs across both sites and 4 waves), the intervention is projected to enroll a minimum of 1,008 subjects into the intervention group. An equivalent number of subjects will be randomly selected from the Control teams for a total of at least 2,016 study subjects overall. The intervention and control subjects will be split across the two study sites. After assuming that we will not be able to reach about 20% (due to missing or incorrect contact information) unreachable rate, and that about 60% will consent to enroll in the intervention, we will randomly select about double the 1,008 subjects (about 2,100) for potential enrollment into the intervention in order to enroll the minimum of 1,008 intervention subjects needed to have adequate statistical power.

Power: In the pre-DM population we estimate the 3-year DM incidence to be 15% (based on preliminary analysis of a similar VA cohort from 2010-2012). Based on our analyses, with 1,008 patients allocated to each of the intervention and control groups, we anticipate having 80% power ($\alpha = 0.05$) to detect a difference in time-to-event (DM incidence) between the intervention and control group.

To assess measures of implementation fidelity, specifically coverage, duration, and frequency of CHW-patient contact, we will base calculations on all patients enrolled. Since we will use all available study data from the electronic medical records, power and sample size considerations do not apply. We will assess content of CHW-patient contact using qualitative methods, hence power and sample size considerations do not apply.

To examine the variation in prediabetes prevalence across NYC neighborhoods, we will use available data from BH at the start of the study, in approximately 19,000 patients. These patients meet the study's previously stated eligibility criteria, with two modifications: patients must have (1) any HbA1c result in the past 5 years and (2) an address available in the EHR. Data on all enrolled BH patients at the end of the study, an estimated 1,000 patients, will also be used. Since we will use all available study data, power and sample size considerations do not apply.

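### The planned 1,100 per arm does not follow from the stated outreach rates, which give 1,008, and the equal site split conflicts with the stated VA pool of 1,100

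*Combined protocol and SAP*

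**What the plan says.** **Number of Subjects.** The intervention arm is to be filled by "contacting 2,100 randomly selected patients (1,050 at the VA* and 1,050 at BH) to ultimately enroll about 1,100 patients", 550 from each site. The stated basis is that "20% of patients will be unreachable and that 60% of those reached will enroll in the study". A control group of 1,100 is set to match, for a total of about 2,200. The section adds: "This amounts to approximately 265 patients (across intervention and control groups) per wave and per clinical site".

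**Statistical Power and Sample Size.** Here the intervention arm comes from staffing: "Assuming a caseload of 72 patients per fulltime CHW per wave (with 3.5 fulltime equivalent CHWs across both sites and 4 waves"). The result is at least 1,008 per group and at least 2,016 overall. The same two rates are repeated, and about 2,100 patients are to be selected "in order to enroll the minimum of 1,008 intervention subjects needed to have adequate statistical power". The 80% power statement uses 1,008 per group.

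The same section says that the eligibility criteria "return about 9,300 eligible patients, 8,200 at BH and 1,100 at the VA". This VA pool of 1,100 is a different quantity from the 1,100 per arm, although the number is the same.

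**Elsewhere.**
- The Intervention Group section says that patients offered coaching come from the intervention teams at each hospital.
- The CHW Intervention section selects about 250 patients per site per wave and allows decliners to be invited again in later waves.
- The Inclusion Criteria date the HbA1c window from the start of each wave.
- The note under Number of Subjects gives a quarter of dual-eligible VA patients to another study.

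**The concern.** Two sections use the same number of contacts and the same rates, yet one arrives at 1,100 and the other at 1,008. The per-wave figure fits neither total. A reader cannot tell which sample size the trial is committed to, or against which figure a recruitment shortfall should be judged.

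The second matter is separate. The site split takes half of the contacts from the VA, and the VA pool stated in the power section is barely larger than the number of VA patients to be contacted in the intervention teams alone. Controls must come from the same pool. The power section calls 1,008 the minimum for adequate power, so it matters whether the VA can supply its share.

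**Working it through.** **1. Enrolment from the outreach sample**

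Inputs (Number of Subjects): 2,100 contacted, 20% not reached, 60% of those reached enrol.

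- Yield per contact: 0.80 × 0.60 = 0.48.
- Enrolled: 2,100 × 0.48 = **1,008**, or 504 per site if split equally.
- Stated 1,100: excess 1,100 − 1,008 = 92 per arm, 92 / 1,008 = 9.1%. Over both arms, 2,200 − 2,016 = 184.
- Other readings of the rates do not rescue 1,100. Taking 60% of everyone contacted gives 1,260, and subtracting both losses from the total gives 2,100 × 0.40 = 840.

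The power section's own figure reproduces exactly by both of its routes: 72 × 3.5 × 4 = 1,008, and 1,008 / 0.48 = 2,100.

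**2. Per wave and site** (4 waves × 2 sites = 8 cells)

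| Total | Per wave and site |
|---|---|
| 2,200 | 2,200 / 8 = 275 |
| 2,016 | 2,016 / 8 = 252 |
| 265 × 8 = 2,120 | 265 (stated) |

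The stated 265 is close to 2,100 / 8 = 262.5, the number of outreach contacts per cell. It may be an outreach figure with the wrong label, but that is only a guess.

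**3. What 1,100 would require**

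- Contacts: 1,100 / 0.48 = 2,292.
- Caseload at 3.5 full-time equivalents: 1,100 / (3.5 × 4) = 78.6, about 79 per full-time CHW per wave instead of 72.
- Or staffing at a caseload of 72: 1,100 / (72 × 4) = 3.8 full-time equivalents.

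**4. VA demand against the stated VA pool**

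Inputs: 1,050 VA contacts (Number of Subjects) and a VA pool of 1,100 (power section). The number of VA controls is not stated; 504 to 550 is inferred from the equal split.

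- Demand if every contact is a different patient: 1,050 + 504 = 1,554, up to 1,050 + 550 = 1,600.
- If all 1,100 were contacted: 1,100 × 0.48 = 528 enrolled, with nobody left as a control.
- Re-invitation, extreme case in which every reached decliner later enrols: 504 / 0.80 = 630 distinct contacts, and 630 + 504 = 1,134. That is close to the pool. The documents give no acceptance rate for second invitations.
- Dual-eligible patients: the 1,100 is what the eligibility criteria return, so it reads as a count before the allocation to the other study. Afterwards it lies between 1,100 × 0.75 = 825 (all dual-eligible) and 1,100 (none).
- Patients who become eligible at later waves would add to the pool. The documents give no figure.

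**The case against.** **The totals are a floor and a target.** The power section gives 2,016 as a minimum, and 2,200 satisfies it. The CHW Intervention section also has outreach continue until caseloads are full, so the 1,100 drives neither operations nor power. The point about consequences stands. It does not rescue the figure: the same 2,100 contacts and the same rates cannot yield both numbers, and full caseloads amount to 1,008. The Implementation Research section expects about 1,000 enrolled intervention patients, which also fits 1,008.

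**The VA shortage is not shown.** This stands. The equal split appears in Number of Subjects (and in the equal outreach per site under CHW Intervention), while the power section says only that patients will be divided between the sites. A reader might put the shortfall in the VA intervention teams at 80 to 500 patients (630 − 550 to 1,050 − 550). That range needs a pool fixed at 1,100, nobody newly eligible over the waves, and half of VA eligibles in intervention teams. The documents state none of these.

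**The pool split can be reconciled.** A reader might go further and infer that the site figures are impossible. The section starts thus: "we begin with the total accessible population of about 46,000 primary care patients served at the two sites". Taking Bellevue (BH) as 30,000 (Purpose of the Study) and the VA as the remaining 16,000, and applying the 70% and 40% at each site, gives BH 30,000 × 0.85 × 0.28 = 7,140, below the stated 8,200. The VA comes to 16,000 × 0.75 × 0.28 = 3,360, so 67% would have to be removed for age to leave 1,100. The documents do not support this inference. The statement that "about 70% will have had the HbA1c test in the last 2 years and that about 40% of these" are in the prediabetes range describes the pooled eligible group, and only the diabetes share is given by site. The Background section has lower VA rates (62% tested, 18% of those prediabetic). With those rates, and assumed over-75 shares of 18% at the VA and 10% at BH:

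- VA: 16,000 × 0.75 × 0.82 × 0.62 × 0.18 = about 1,098.
- Pooled: (9,840 + 22,950) × 0.28 = about 9,181, within 1.3% of 9,300.

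The over-75 shares are assumptions, but they show that the stated split is attainable. Nor does the Background count of 1,730 VA patients contradict 1,100: it dates from 2010-2012 and reflects age, diabetes and HbA1c only, whereas the trial's criteria also cover language and medication.

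**Conclusion.** The enrolment figure is wrong on its own terms. The stated rates give 1,008 per arm and 2,016 in total; 1,100 and 2,200 are about 9% too high, and 265 per wave and site fits neither total. This rests only on the protocol's own numbers. The outreach rates bear on the intervention arm alone; the control figure is affected because it is set to match. A reader might infer that the trial loses power if 1,100 becomes 1,008. It does not lose stated power, because the power statement already uses 1,008.

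The VA point is a conflict between stated figures: 1,554 to 1,600 patients called for against a pool of 1,100. It assumes an equal split of controls and a different patient for each contact. It is not a demonstrated shortage, because re-invitation and wave-by-wave eligibility could narrow the gap by an amount that the documents leave open.

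**What to change.** **Sample size.** In Number of Subjects, state 1,008 per arm, 2,016 in total and, if the split stays equal, about 252 per wave and site. If 1,100 is intended, keep it and state what it needs: about 2,292 contacts and about 79 patients per full-time CHW per wave.

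**VA pool.**
- Recount VA eligibles from the registry by arm and wave, net of the dual-eligible allocation.
- Say whether the 2,100 are distinct patients or include repeat invitations.
- State the testing rate, prediabetes rate and over-75 share used at each site, so that the 8,200 and 1,100 can be followed.
- Set site targets that the count can supply.

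**Cost.** Edited figures and a registry count, with no additional patients. The stated total falls from 2,200 to 2,016. If the count confirms a VA pool near 1,100 and targets move towards BH, shifting CHW time between sites would be a real cost, since CHWs are recruited from each site's own patient organisations.
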